5.1.6. Processing of missing date and missing data

Except for special circumstances, the following rules for imputation are applicable to the absence of event date for safety data.

If the date of an event is totally absent, it will not be imputed. If the date is missing, but the year and the month are consistent with that of study treatment, it will be imputed with the date of the first dose of the investigational drug, or first day of that month for other conditions; if the date of the end day is missing, but the year and the month are consistent with that of the end of treatment, the date of the end of event will be imputed with the date of the end of study treatment, or the last day of that month for other conditions.

If the month and the date of an event are missing, but the year is consistent with that of study treatment, they will be imputed with those of the start of study treatment, or 1 Jan. for other conditions.

All the dates imputed must precede the dates of withdrawal of informed consent form, lost to follow-up or death.

Missing data on laboratory tests, ECG, and vital signs will not be imputed.

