9.1 Adverse Events

9.1.1 Definition of AE

AE is defined as adverse medical event that occurs after the subject who receives a drug in clinical trial, but do not necessarily have a causal relationship with the treatment. Any AE from the signature of informed consent form to 90 days after the last dose will be collected. AE can be any undesirable and unexpected symptom, sign, laboratory abnormal or disease, including at least the following conditions:

- 1) Aggravation of existing (prior to enrollment of clinical trial) medical condition/disease (including exacerbation of symptoms, signs, abnormal laboratories);
- 2) Any new occurrence of AE: any adverse medical condition newly occurs (including symptom, signs, newly diagnosed diseases);
- 3) Abnormal laboratory test or result of clinical significance.

The investigators should carefully record any AE occurs in the subjects, including: description of adverse event and relevant symptoms, time of onset, severity, causality with investigational drug, duration, actions taken, final outcomes and prognosis.

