5.5.2. Treatment-emergent adverse events (TEAEs)

Adverse events will be summarized using descriptive statistics according to Hengrui's Statistical Analysis Reporting Standards, including but not limited to:

- Overview of adverse events (all-cause and treatment-related);
- Summary of serious adverse event;
- Incidence and severity of adverse event (all-cause and treatment-related);

- Causality between adverse event and investigational drug;
- Selected related adverse events (endocrine, gastrointestinal, liver, lung, kidney, hypersensitivity/infusion reaction, and skin);
- Adverse events of special interest.

Adverse events of special interest mainly include:

- Hemangioma (time to event and duration of event, outcome, recovery, or remission)
- Grade ≥ 3 infusion reaction
- Grade ≥ 2 diarrhea/colitis, uveitis, and interstitial pneumonia
- Grade ≥ 3 other immune related adverse events: skin, gastrointestinal, lung, endocrine (by system organ class)
- Abnormal hepatic enzyme: abnormal ALT, AST, and total bilirubin from baseline
- Grade 4 amylase or lipase increased

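### SAP 5.1.6 imputes partial adverse event dates without checking the event's other date, so an event can end before it starts

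*SAP*

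**What the plan says.** SAP 5.1.6 opens by setting its scope: "Except for special circumstances, the following rules for imputation are applicable to the absence of event date for safety data". The special circumstances are not defined. Its rules are then:

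- **Start, day missing.** If month and year match study treatment, the rule is that "it will be imputed with the date of the first dose of the investigational drug, or first day of that month for other conditions".
- **End, day missing.** If month and year match the end of treatment, "the date of the end of event will be imputed with the date of the end of study treatment"; otherwise the last day of the month is used.
- **Day and month missing.** If the year matches study treatment, "they will be imputed with those of the start of study treatment, or 1 Jan. for other conditions". This sentence does not say whether it covers start dates, end dates or both.
- **Bound.** "All the dates imputed must precede the dates of withdrawal of informed consent form, lost to follow-up or death". No other limit is given.

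On the collection window, Protocol 9.1.1 states: "Any AE from the signature of informed consent form to 90 days after the last dose will be collected". Protocol 3.2.1 allows up to 28 days of screening before the first dose. SAP 4.2.1 counts events during follow-up as TEAEs and defines a TEAE by occurrence or worsening after treatment, without mentioning the end date. SAP 5.5.2 plans one output that uses event length: "Hemangioma (time to event and duration of event, outcome, recovery, or remission".

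**The concern.** The collection window is wider than the treatment period at both ends. An event can start after treatment has stopped, or be over before the first dose, and still be in the database. The imputation rules tie partial dates to the first dose and to the end of treatment as though events lay between them. When an event lies outside, the imputed date falls on the wrong side of the date that is known.

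Two things are at stake. Durations can be zero or negative, which is impossible and would distort any summary of duration. An event that ended before exposure can also be given an onset on the first-dose date, which may bring it into the TEAE tables. An analyst who follows the SAP to the letter gets impossible records; one who repairs them makes choices that the SAP does not document.

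**Working it through.** SAP 5.1.6 contains no numerical figure to reproduce. The check applies its rules literally to example dates.

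**Inputs.** The rules and the bound are from SAP 5.1.6, and the collection window is from Protocol 9.1.1. The example dates are assumed: first dose 15 Mar 2017, end of treatment 10 Sep 2017, death 1 Dec 2017. The SAP gives no formula for adverse event duration; end - start + 1 is assumed.

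| Case | Recorded start | Recorded end | Imputed date | Duration (days) |
|---|---|---|---|---|
| Control | 2 Sep | Sep, day missing | end 10 Sep | 10 - 2 + 1 = 9 |
| A | 20 Sep | Sep, day missing | end 10 Sep | 10 - 20 + 1 = -9 |
| B | Mar, day missing | 8 Mar | start 15 Mar | 8 - 15 + 1 = -6 |
| C | 2017 only | 8 Mar | start 15 Mar | 8 - 15 + 1 = -6 |
| D | 1 Jul | 2017 only | end 15 Mar, if the year-only rule is applied to end dates | -108 + 1 = -107 |

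The control shows that the end rule works when onset precedes the end of treatment. In case A the event ends 10 days before it begins. In cases B and C it begins 7 days after it ended. All the imputed dates precede the assumed death on 1 Dec, so the SAP's bound catches none of them.

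**When reversal is certain.** End rule: a known start falls after the end of treatment in the same month and the end day is missing. Start rule: a known end falls before the first dose and the partial start matches the first-dose month (or year, when only the year is known).

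**How often, given a record within reach of a rule.** Suppose the treatment day and the known event day are independent and uniform over a 30-day month. The reversed pairs then number 30 x 29 / 2 = 435 of 900, or 48.3%, under each day-missing rule. The worst duration is 1 - 30 + 1 = -28 days. This is conditional on one partial and one known date in the relevant month; it is not a share of all adverse events.

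**Share of all records.** The documents give no rate of partial dates. Assume that 1-5% of adverse event dates lack a day and that 20-30% of those fall in the first-dose or end-of-treatment month. Then 1% x 20% = 0.2% and 5% x 30% = 1.5% of records are touched by the day-missing rules. Only some of these would be reversed, so the range is a ceiling under those assumptions. Year-only dates are outside it.

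**With order constraints added.** Case A: end = max(10 Sep, 20 Sep) = 20 Sep, duration 1 day. Cases B and C: start = min(15 Mar, 8 Mar) = 8 Mar, duration 1 day, onset before first dose. Case D does not arise if the year-only rule is confined to start dates.

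**The case against.** **Data cleaning.** Protocol 10.1.1 to 10.1.3 provide for logic checks on entry, repeated queries, a data verification meeting before lock and full monitoring of source documents, including adverse event records. These should keep partial dates rare, and that stands. They act on entered data, however, whereas the reversal is created afterwards by the imputation.

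**Room for exceptions.** The opening words of SAP 5.1.6 allow special circumstances. Since these are undefined, they cannot serve as a rule on date order.

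**Conservatism.** Placing an unknown onset at the first dose is a usual and cautious choice when the end is unknown or falls on or after the first dose. This stands. The fault is limited to the missing check against a known earlier end.

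**TEAE status.** A reader might infer that events resolved before treatment will be counted as TEAEs. The documents do not establish this. SAP 4.2.1 does not say that the flag is computed from the imputed onset alone, or that onset on the first-dose day counts as after treatment. An event with a recorded end before first dose does not meet the definition in substance. The misclassification is possible, not certain. The pre-dose window may also be short: SAP 4.2.1 speaks of consent and enrollment, and if enrollment means randomization, that falls within 3 days before the first dose. The protocol's window runs from consent.

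**The end-of-treatment convention.** A reader might conclude that it should be replaced by the last day of the month throughout. The reversals do not require that; it is a preference about which convention to use.

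**Consequence.** Most planned adverse event outputs are incidence, severity and causality, which do not use end dates. Safety is summarised descriptively. This stands and keeps the point small.

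**Conclusion.** The point holds as a defect in the stated rules. Read literally, SAP 5.1.6 can give an end before a known start and a start after a known end, and its only bound prevents neither. The year-only sentence has the same weakness and can set an end date to the start of treatment.

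The size is minor. The range of 0.2-1.5% rests on assumed rates and describes records touched by the day-missing rules; it should not be read as the share that is wrong. Hemangioma is the only event for which a duration output is named, and ORR and 6-month OS are unaffected. The effect on TEAE counts depends on how the flag is programmed, which the SAP leaves open. The reading also takes the start rule to refer to event onset; its wording says only the date, but the imputed value and the separate end-date clause make that the natural sense.

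**What to change.** In SAP 5.1.6, keep the existing imputation rules and the existing bound (withdrawal of consent, loss to follow-up, death), and add:

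1. An imputed end date is never earlier than the known start date.
2. An imputed start date is never later than a known end date.
3. Only an event whose known end, full or partial, is definitely before the first dose is excluded from TEAEs. Events that are ongoing, or whose end is unknown, keep the first-dose imputation and remain TEAEs.
4. The year-only rule applies to start dates only.

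The wording of item 3 matters. A rule that used the first-dose date only when a known end falls on or after it would remove ongoing and undated events from the TEAE count, exchanging a rare over-count for an under-count in the safety tables. Item 4 leaves year-only end dates without a rule, so the SAP should say that they stay missing or state a separate convention.

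The cost is a few sentences and a few program conditions. No data collection or trial procedure changes.

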5.2. Study Subjects

All summaries will be performed by group and overall.

5.2.1. Disposition of subjects

The number and percentage of subjects will be summarized, the number and percentage of subjects included in each analysis set will be summarized, and the number and percentage of subjects in each period during the study will be summarized, for example, the number of subjects enrolled after randomization, number of subjects who have completed the study, as well as the number and percentage of subjects who interrupt treatment and withdraw from the study prematurely for various reasons.

5.2.2. Demographics

Age, gender, ethnicity, height, weight, and body mass index of subjects will be descriptively summarized. Continuous variables, including age, height, weight, and body mass index, will be summarized with descriptive statistics, including number of evaluable subjects (n), mean, standard deviation, median, minimum (Min), and maximum (Max). Categorical variables, including gender and ethnicity, will be descriptively summarized with the number of evaluable subjects in each category and corresponding percentage in the total number. Baseline characteristics are also summarized for sub-populations.

5.2.3. Medical history

The previous history of tumors (extrahepatic metastasis, HBV infection, Child-Pugh score (5, 6, 7), AFP \geq 200 NG/mL or AFP < 200 NG/mL, AFP \geq 400 NG/mL or AFP < 400 NG/mL, and BCLC stage) and history of treatment will be statistically described correspondingly by treatment group.

All the previous history of general diseases will be listed.

5.2.4. Prior therapy and concomitant medication

These will be summarized based on the classification of clinical departments. Prior anti-cancer therapy: surgical therapy, local therapy, radiotherapy, systemic therapy (1 line, 2 lines, \geq 3 lines of therapies); the systemic treatment includes systemic chemotherapy and targeted therapy.

The systemic treatment will be classified and tabulated by the type of therapy and generic name.

All prior and concomitant medications will be classified and tabulated by the type of therapy and generic name.

5.2.5. Protocol deviations

Before the database is locked, all subjects' data on the CRF will be checked for important protocol deviations. All possible critical or major protocol deviations will be evaluated by the investigator and the sponsor.

All critical or major protocol deviations will be summarized and described by types, and analyzed in listing.

Critical or major protocol deviations include, but are not limited to:

- Serious violation of the eligibility criteria;
- Wrong assignment into treatment groups;
- Use of prohibited drug during treatment;
- Poor compliance (compliance rate < 50%).

5.3. Treatment Compliance

The use of the investigational drug will be descriptively summarized.

All subjects will be listed by treatment groups. The contents to be listed include but are not limited to treatment period, date of administration, and actual dose administered.

5.4. Efficacy Analysis

The efficacy analysis will be performed separately by group and overall.

Efficacy analysis will be based on IRC-assessed data and investigator-assessed data, with the former as the primary analysis.

Based on the FAS, PPS, and ES, ORR and 95% CI will be calculated separately by group and overall. The CI will be calculated using the Clopper-Pearson method. In addition, the difference in ORR will be calculated between the two groups, and Wald method will be used to estimate the 95% CI of the difference, and the nominal P value will be calculated based on Pearson Chi-square test.

In addition, based on the FAS, Amit method will be used to analyze the discrepancy between IRC-assessed and investigator-assessed PD/non-PD, BOR, and CR/PR.

Based on the FAS and PPS, Kaplan-Meier method will be used to calculate the 6/9/12-month OS% and the corresponding 95% CIs will be calculated.

Based on the FAS, the secondary efficacy endpoint PFS (including the 6/9/12-month PFS rate), TTP, OS, and DoR will be analyzed using Kaplan-Meier method. TTR will be descriptively summarized. When applicable, the survival curve will be plotted by endpoints. For PFS, TTP, OS, and DoR, the hazard ratios between groups and their 95% CIs will be computed using the COX proportional hazards model and nominal P values will be calculated using the log-rank test.

For the secondary efficacy endpoint DCR, the same statistical method with ORR will be used for analysis based on the FAS, the PPS, and the ES.

The best overall response (BOR) will be summarized.

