2.3. Sample Size

Referring to the study results on similar products, assuming the ORR is 15% for SHR-1210 in treatment of target population of this study, and the lower limit of 95% confidential interval of ORR obtained from this study is >7%, it can be considered as effective. 154 subjects need to be enrolled to obtain 90% power at a one-sided significance level of 0.025. Further assuming evaluable cases accounting for 80% of the enrolled subjects, 194 subjects are required to be enrolled.

Assuming the survival rate at 6 months is 80% for SHR-1210 in treatment of target population, and the lower limit of 95% confidential interval is >70%, this therapy can be considered to have advantage in efficacy. 200 subjects need to be enrolled to obtain 90% power at a one-sided significance level of 0.025. Considering the drop-out rate of 10%, a total of 220 subjects are required to be enrolled.

Considering the above two points, a total of 220 subjects will be enrolled in the study.

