5.4.2. Subgroup analysis

Based on the FAS, subgroup analysis will be conducted merely on OS. The median OS and their 95% CIs will be provided for each subgroup. Forest plot will be prepared when necessary. The definition of subgroup is presented in section 5.1.4.

Based on the FAS, relevant efficacy endpoint analyses will be performed for sub-populations A, B, C, D, and E, with the same analytical method as above. The objective response swimmer plot and survival curves will be plotted for each sub-population.

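### The Wald interval for the Q2W–Q3W difference in ORR would be unreliable in any of sub-populations A–E that has about 15 or fewer subjects per arm, or small unequal arms

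*SAP*

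**What the plan says.** SAP 5.4 treats single proportions and their difference by different methods. For ORR in each group and overall, "The CI will be calculated using the Clopper-Pearson method". For the contrast between the Q2W and Q3W groups, the "Wald method will be used to estimate the 95% CI of the difference", and beside it "the nominal P value will be calculated based on Pearson Chi-square test".

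Two further sentences extend this. In SAP 5.4, "For the secondary efficacy endpoint DCR, the same statistical method with ORR will be used". In SAP 5.4.2, "relevant efficacy endpoint analyses will be performed for sub-populations A, B, C, D, and E, with the same analytical method as above". Section 5.4 opens with "The efficacy analysis will be performed separately by group and overall", so the method carried into A–E would normally include the between-group difference. SAP 5.4.2 does not say so outright.

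SAP 5.1.4 defines A–E by type of prior therapy and number of lines, and gives no expected sizes. The SAP sets no minimum size and no alternative for sparse data. SAP section 3 says that the analyses are mainly descriptive, without formal testing, and ties the efficacy conclusion to the overall intervals for ORR and 6-month survival.

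**The concern.** The Wald interval takes its standard error from the observed proportions. When few subjects respond, that standard error is itself poorly estimated and often too small. When neither arm has a responder it is zero, and the interval reports a difference known exactly to be nil. The SAP avoids this for single proportions by using an exact interval, but not for the difference.

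The schedule comparison is the only randomised contrast in the trial. In a small sub-population, an ORR interval that is too narrow would make the two schedules look more firmly different, or more firmly alike, than the data allow. It can also disagree with the P value printed beside it. With 3/10 against 0/10 responders, the Wald interval is 0.016 to 0.584 and excludes zero, while the Pearson chi-square P value is 0.060.

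**Working it through.** **Inputs.** The ORR of 15% comes from SAP 2.3 ("assuming the ORR is 15% for SHR-1210 in treatment of target population of this study"). The 7% benchmark comes from the same section. Allocation is 1:1 among 220 subjects (SAP 2.1), about 110 per arm. The rate pairs 15/15, 15/5, 15/7 and 20/10%, the sub-population sizes and a DCR of 50% are assumptions; the documents give none of them.

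**The plan's own figure.** The SAP has no figure for the difference. Its ORR sample size does reproduce with the exact method: at n = 154 the Clopper-Pearson lower limit exceeds 7% from 18 responders upward. The one-sided error is then 0.0227 and the power at 15% is 0.9002.

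**Formulas.** With observed proportions p1 and p2 and difference d = p1 − p2:

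- Wald: d ± 1.96·√[p1(1−p1)/n1 + p2(1−p2)/n2].
- Newcombe: with Wilson limits (l, u) for each arm, from d − √[(p1−l1)² + (u2−p2)²] to d + √[(u1−p1)² + (p2−l2)²].
- Coverage: the sum, over all pairs of responder counts, of the product of the two binomial probabilities for pairs whose interval contains the true difference.

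**Wald coverage for ORR (%), equal arms.**

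| Per arm | 15/15 | 15/5 | 15/7 | 20/10 |
|---|---|---|---|---|
| 110 | 94.8 | 95.0 | 94.6 | 94.9 |
| 30 | 94.1 | 92.6 | 93.3 | 94.3 |
| 15 | 95.9 | 90.2 | 88.6 | 93.6 |
| 10 | 92.2 | 79.6 | 84.9 | 87.5 |

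At 40 per arm coverage is 93.5–94.7%, and at 20 per arm 93.6–94.4%. The largest shortfall at 20, 30 or 40 is therefore 95 − 92.6 = 2.4 points. Coverage moves irregularly with n: over every size from 20 to 40 the lowest value is 92.1%, at 21 per arm with 15/7.

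**Unequal arms of 10 and 20.** Coverage is 91.0% at 15/15. It is 78.7% when the arm of 10 has a true rate of 15% and the arm of 20 has 7%. With those two rates swapped it is 93.8%, so imbalance harms mainly when the smaller arm does not have the lower rate.

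**Zero width.** For ORR this needs, in practice, no responder in either arm. At 10 per arm:

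- 15/15: 0.85^20 = 3.9%
- 15/7: 0.85^10 × 0.93^10 = 9.5%
- 15/5: 0.85^10 × 0.95^10 = 11.8%
- 20/10: 0.80^10 × 0.90^10 = 3.7%

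At 30 per arm it is at most 0.16%.

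**Newcombe in the same settings.** Coverage is at least 95.2% in every cell of the table and for arms of 10 and 20. For 0/10 against 0/10 the Wilson upper limit is 3.84/13.84 = 0.278, so the interval is −0.28 to 0.28, where Wald gives 0 to 0. For 3/10 against 0/10 it is −0.038 to 0.603, in line with the P value of 0.060.

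**DCR, assumed 50% in both arms.** Wald coverage is 95.0% at 110 per arm, 94.8% at 30, 91.9% at 20 and 91.2% at 10. The mean Wald width at 10 per arm is 0.83 against 0.72 for Newcombe, and zero width has a probability near nil.

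**The case against.** The strongest reply is that nothing in the documents shows any of A–E to be this small. Ten per arm means about 20 of 220 subjects. Prior sorafenib or chemotherapy is the main entry route (protocol 5.1), so A is probably most of the full analysis set. D and E, one standard treatment against two or more lines, roughly divide the treated subjects and are unlikely both to be tiny. At 55 per arm Wald coverage is 93.8–94.5%. This stands, and it makes the point conditional on size.

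The SAP revision table says that the sub-populations were added for comparison with other drugs. That use rests on the response rate within each sub-population, which has an exact interval. SAP 5.4.2 also refers only to relevant analyses, so use of the Wald difference in A–E is implied rather than stated. This stands too, though nothing in the text excludes the difference.

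No decision uses the interval, and its P value is labelled nominal. The separate exact intervals would also expose a zero-width result: for 0/10 the upper limit is about 31%. This limits the consequence, but it does not make the Wald interval a good choice for sparse ORR data.

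A reader might infer that DCR shares the same fault, since it takes the ORR method. It does not. DCR counts stable disease, so few responses is the wrong description, and at mid-range rates the Wald interval is wider on average than Newcombe's. Only some under-coverage in small arms remains.

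**Conclusion.** The point holds as a minor, conditional one. The SAP's Wald interval for the ORR difference is adequate for the whole trial and loses little in equal arms of 20–40. It under-covers clearly, and can collapse to zero width, only where a sub-population has about 15 or fewer subjects per arm or has small unequal arms. Even there the loss is mainly when the true rates differ; at 15/15% with 15 per arm, coverage is 95.9%.

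The result rests on assumed sub-population sizes, on true ORRs near the planned 15%, and on reading SAP 5.4.2 as including the between-group difference. The DCR figure rests on an assumed rate of 50%.

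Two stronger readings go beyond the documents. One is that the intervals in A–E will be too narrow; without sizes this cannot be said of any named sub-population. The other is that the trial's efficacy conclusion is at risk; SAP section 3 bases that on the overall intervals, which do not use this method.

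**What to change.** In SAP 5.4, replace the Wald method with the Newcombe hybrid score interval (or Miettinen–Nurminen) for the between-group difference in ORR, and name the same method for DCR so that the two endpoints match. In SAP 5.4.2, say whether the difference is to be reported in each of A–E.

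The cost is one phrase in the SAP and one option in the program. In the whole trial the result hardly changes: for 16/110 against 17/110, Wald gives −0.104 to 0.085 and Newcombe −0.105 to 0.087. In small sub-populations the ORR intervals become wider and somewhat conservative. At 10 per arm Newcombe coverage is 97.7–99.1%, and the mean width rises from 0.57 to 0.65 at 15/15% and from 0.48 to 0.63 at 15/7%.

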8.2 Secondary Endpoints and Observation Method

- 1). Duration of response (DoR): defined as the time from the date of first record of objective response (CR or PR) to the first occurrence of progression or death.
- 2). Time to progression (TTP): defined as the time from the date of randomization to any documented radiological tumor progression.
- 3). Disease control rate (DCR): defined as the percentage of subjects with CR, PR and SD (≥ 6 weeks) in the evaluable population.
- 4). Progression-free survival (PFS): defined as the time from randomization to any documented radiological tumor progression or death.
- 5). Overall survival (OS): defined as the time from randomization to death from any cause.

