2.1. Study Design

This is a randomized, open-label, multi-center, phase II study. The primary objective is to evaluate the efficacy and safety of SHR-1210 in subjects with advanced HCC after failure of previous systemic treatment. A total of 220 subjects will be enrolled and randomized in a 1:1 ratio to receive SHR-1210 3 mg/kg, I.V., Q2W (once every two weeks) or SHR-1210 3 mg/kg, I.V., Q3W (once every three weeks) group, in 42-day cycles.

The study design schematic is presented in the following figure:

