3. STATISTICAL HYPOTHESIS

All analyses will be primarily based on descriptive statistical summary by group and overall. No formal statistical hypothesis testing will be performed. The overall 95% CIs of the two primary study endpoints, ORR and 6-month OS rate, will be calculated. The lower limit of the overall 95% CI of ORR is > 7% and the lower limit of the overall 95% CI of 6-month OS rate is >70% indicate that the drug is effective.

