4.1.2. Duration of response (DoR)

Defined as the period from the first documentation of CR or PR to the first documentation of PD or to death due to any reason in subjects with confirmed CR or PR. If no PD or death occurs, it will be censored at the last tumor assessment.

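### The planned Q2W-versus-Q3W hazard ratio and log-rank P for duration of response compare responders only, so randomisation does not protect them and they can mislead in either direction (minor)

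*SAP*

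**What the plan says.** SAP 5.4 groups DoR with three endpoints that every FAS subject has: "Based on the FAS, the secondary efficacy endpoint PFS (including the 6/9/12-month PFS rate), TTP, OS, and DoR will be analyzed using Kaplan-Meier method". It then plans the comparison between the two schedules: "For PFS, TTP, OS, and DoR, the hazard ratios between groups and their 95% CIs will be computed using the COX proportional hazards model", and adds that "nominal P values will be calculated using the log-rank test". Table 1 in SAP 5.1.1 also assigns DoR to the FAS. No responder set is defined, and nothing is said about how the DoR comparison should be read.

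SAP 4.1.2 restricts the endpoint. DoR runs from the first documented response to progression or "to death due to any reason in subjects with confirmed CR or PR". Protocol 8.2 uses the same starting point: "defined as the time from the date of first record of objective response (CR or PR) to the first occurrence of progression or death".

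Two other statements set the weight of the point. SAP 2.1 says: "A total of 220 subjects will be enrolled and randomized in a 1:1 ratio". SAP 3 says: "No formal statistical hypothesis testing will be performed". The efficacy criteria in SAP 3 are lower 95% limits above 7% for overall ORR and above 70% for the overall 6-month OS rate. DoR has no part in them.

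**The concern.** For PFS, TTP and OS, the comparison of Q2W with Q3W uses all randomised and dosed subjects, so it keeps the balance that 1:1 allocation provides. DoR does not. A subject enters the DoR analysis only by responding, and the dosing schedule may affect who responds. If the schedules produce different numbers of responders, the two responder groups differ in composition, and a hazard ratio between them mixes the effect of the schedule with that difference.

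The output would nevertheless look the same as the PFS and OS output: a hazard ratio, a 95% CI and a P value, under the FAS label. What is at stake is the descriptive comparison of the two schedules on durability. SAP 5.4 runs efficacy analyses on both independent-review and investigator data, and SAP 5.4.2 applies the same methods to relevant endpoints in sub-populations A to E. If DoR counts as relevant there, the same ratio is repeated on still fewer responders.

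**Working it through.** **The plan's own figures.** The documents give no figure for the DoR comparison. The ORR input of 15% comes from the sample-size calculation in SAP 2.3, which reproduces. With 154 subjects, the Clopper-Pearson lower limit exceeds 7% from 18 responses upward; the exact one-sided alpha is 0.0227 and the power at 15% is 0.9002. For 6-month OS, 200 subjects need 153 survivors; alpha is 0.0249 and power 0.9056. Neither calculation concerns a difference between arms.

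**Expected number of responders.** 220 × 0.15 = 33, or 16.5 per arm if the rates are equal. The 95% binomial range for one arm of 110 is 10 to 24.

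**Precision.** With equal event numbers per arm, the 95% CI factor is exp(1.96 × √(4/events)).
- 10 events: 3.45
- 15 events: 2.75
- 20 events: 2.40
- all 33 responders with an event: 1.98

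Power to detect a true hazard ratio of 0.5 is 19% with 10 events, 34% with 20 and 51% with 33.

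**Direction and size.** The documents give no per-arm ORR, DoR median or censoring pattern, so these are assumptions. Both arms share the same core responders, with exponential DoR and a 12-month median. Arm A adds a fraction k of further responders with median m. All are censored at 12 months. Per core responder, arm B has S_B(t) = 2^(−t/12) still in response, and arm A has S_A(t) = 2^(−t/12) + k·2^(−t/m). Let f_A and f_B be the corresponding event densities. The large-sample Cox estimate b solves ∫ [f_A − p(t)(f_A + f_B)] dt = 0 over 0 to 12 months, with p(t) = S_A·e^b / (S_A·e^b + S_B). The hazard ratio, A to B, is e^b:

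| Median of added responses | k = 25% | k = 50% | k = 100% |
|---|---|---|---|
| 4 months | 1.25 | 1.44 | 1.72 |
| 8 months | 1.09 | 1.15 | 1.23 |
| 12 months | 1.00 | 1.00 | 1.00 |
| 18 months | 0.93 | 0.88 | 0.82 |

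Hand check for k = 100%, m = 4. At time 0, half of arm A's responders have three times the core hazard, so the ratio is (1 + 3)/2 = 2.0. At 12 months, 0.5 of the core and 0.125 of the added responders remain, so the ratio is (0.5 × 1 + 0.125 × 3)/0.625 = 1.40. The Cox value of 1.72 lies between these two.

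**Signal against noise.** Take the most extreme row and column (k = 100%, m = 4) with 33 responders: 11 in arm B and 22 in arm A. Expected events are 11 × 0.5 = 5.5 in B, and 11 × 0.5 + 11 × 0.875 = 15.1 in A, or 20.6 in total. The CI factor is about 2.37, and wider once the unequal split is allowed for. An interval around 1.72 runs from about 0.73 to 4.1.

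**Simulation with other assumptions.** Here 110 subjects per arm were simulated with censoring uniform over 3 to 18 months. Arm A keeps every response that arm B would give and adds shorter ones.
- ORR 18% against 12%: large-sample hazard ratio 1.30 (added median 6 months) or 1.50 (4 months).
- ORR 20% against 10%: 1.45 or 1.70.
- Across these four cases the estimate exceeds 1 in 67% to 86% of trials, and the log-rank P is below 0.05 in 7% to 17%.
- With equal ORR, or added responses as durable as the rest, the ratio is about 1.0.

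**The case against.** The strongest reply is that nothing depends on this ratio. The P value is called nominal, SAP 3 makes the analyses descriptive, and the success rule uses only overall ORR and 6-month OS. DoR is secondary, and the documents contain no rule for choosing a schedule from it. The same section compares the arms on ORR, PFS, TTP and OS in the FAS, so a higher response rate would appear beside any DoR ratio. All of this stands, and it is why the point is minor. These labels deal with multiplicity and confirmatory status, however. They do not make the responder groups comparable.

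A second reply is that the bias needs two conditions together: unequal response rates, and extra responses whose durability differs from the rest. That also stands. A reader might infer from the 4-month row that the analysis penalises whichever schedule produces more responses. The documents do not support that. They give no per-arm ORR and no DoR median, and with more durable extra responses the ratio favours that arm.

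A reader might also infer that the ratio is bound to be taken for a randomised effect. The plan's descriptive wording speaks against this. The risk comes from the FAS label and the missing caveat, and it is a possibility only.

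Finally, a footnote could replace deletion. It would reduce the risk of misreading, but it would leave a ratio with no clear interpretation and a very wide interval.

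**Conclusion.** The point holds as a minor one. SAP 5.4 plans a between-arm hazard ratio, CI and nominal P for an endpoint that exists only in confirmed responders, and it labels the analysis as FAS-based. The comparison is conditioned on an outcome observed after randomisation, so it does not estimate a randomised effect of schedule.

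Under the assumed values the distortion runs from 0.82 to 1.72, and it is absent when both arms have the same responders. Those figures rest on assumed medians, increments and censoring, and illustrate what can happen; they do not predict this trial. With about 33 responders the ratio would be very imprecise in any case. The trial's main conclusion is not at risk.

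**What to change.** In SAP 5.4, take DoR out of the sentence on Cox hazard ratios and log-rank P values. State that DoR is analysed in confirmed responders within the FAS, and align Table 1 in SAP 5.1.1 with that. Report Kaplan-Meier DoR by arm and overall, with the median, its 95% CI and the number of responders.

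If a comparison of durability between schedules is wanted, base it on all FAS subjects. One option is the probability of being in confirmed response at 6 and 12 months from first dose, with non-responders counted as not in response. The SAP must then state how subjects censored before those times are handled, because the result depends on that rule.

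The cost is a small edit to the SAP and, if the optional measure is adopted, one small table. One nominal hazard ratio and its P value are lost.
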